#### **The Berg Balance Scale**

The BBS was designed to measure changes in functional standing balance over time. This is a 14-item scale that rates each function from 0 (worst) to 4 (best). This scale measures balance abilities seen during tasks involving sitting, standing, and positional changes. Total scores are indicative of overall balance abilities, with scores interpreted in the following manner: 0 to 20, wheel-chair bound; 21 to 40, walking with assistance; and 41 to 56, independent. The BBS is relatively safe and simple to administer. It uses a quantitative scale format that has strong internal consistency and good inter- and intra-rater reliability with different patient populations, including brain injury, stroke, and geriatric patients. It has specifically been clinically validated for evaluating postural instability in PD patients.

For this study, improvement will be defined as an 8 point improvement of the scale which has been found in one study to be required to reveal a genuine change in function among older people who are dependent in activities of daily living and living in residential care facilities.

#### **MANAGEMENT OF ADVERSE EXPERIENCES**

The four most common adverse events with varenicline in adult studies are nausea, insomnia, abnormal dreams, and headache. Other side-effects include: constipation, dry mouth, flatulence, and dizziness. Psychiatric side effects have been reported and will be strictly monitored. The four most common placebo side-effects also include: nausea, insomnia, abnormal dreams, and headache. Adverse events will be documented on the adverse event form and sent to the independent medical monitor.

#### **CRITERIA FOR INTERVENTION DISCONTINUATION**

Criteria and rules for stopping subject treatment include: new toxicological findings or serious adverse events, patient withdrawal of consent without need for justification, inability of the patient to participate for medical reasons (such as surgery), violation of eligibility criteria, development of significant neuropsychiatric symptoms such as suicidal ideation or psychosis, subject failure to comply with the protocol, development of cardiovascular symptoms, new cardiovascular diagnosis, or a cardiovascular event. Subjects who stop treatment will still be asked to complete a final visit with rating scales and blood work.

#### **STATISTICAL CONSIDERATIONS**

### General Design Issues

The primary and secondary outcomes will be analyzed using SPSS. The independent medical monitor will review adverse event data and the final analysis. There will be no interim analysis performed. The independent medical monitor will not be blinded to treatment arm. There will be no stratification.

### Outcomes and Data Analysis

- Primary outcome (Aim 1): The primary hypothesis will be tested using a paired *t*-test using means of the total Berg Balance Scale score before and after treatment. Linear regression will be used to determine if there is an association among outcome, gender, age, race, or ethnicity. This outcome will be determined by the rating of patients from a blinded movement disorders neurologist.
- Secondary outcomes (Aim 2): Secondary hypotheses will be tested using paired *t*-tests on the full MDS-UPDRS, the TUG, and the ABC scale. For side effect analysis, logistic regression will be performed with the treatment arm as the dichotomous outcome and the MMSE and FAB as covariates. In addition, gender and age will also be included as covariates.
- Side effects (Aim 3): Adverse events will be recorded and classified as to seriousness of the side effect and likelihood that the side effect is related to the drug. Adverse events in the treated group versus the untreated group will be compared and any events that are significantly more frequent in the treated group will be identified.
- Sample Size and Accrual: Sample size was estimated using published means and standard deviations of the BBS in PD subjects. The mean of the rating scale is 40.22 with a standard deviation of 8.48. Based on a published effect size of a change of 8 points, and using a power of 0.80 and a significance of 0.05 with a two sided test, a sample size of 19 subjects for each group would be needed for a parallel design. To allow for attrition, 42 subjects will be recruited. Intent to treat analysis will be performed. The number of subjects lost to follow-up is likely to be low due to the relative lack of efficacy of other forms of treatment for this particular symptom of PD. Power for calculating secondary outcomes is lower than 0.8.

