## STUDY OBJECTIVES

### Primary Objective

The hypothesis tested is that varenicline will result in improvement of balance and postural instability after eight weeks of treatment compared to placebo. The null hypothesis is that there will be no difference in tests of balance between subjects on placebo compared to those on varenicline using the Berg Balance Scale as the primary outcome. The primary and secondary outcomes will be performed by the site investigator who will be blinded to treatment.

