### STUDY DESIGN

This is a randomized, double blind, placebo controlled parallel-designed study. Varenicline was chosen because of its novel mechanism of action and its preliminary success in treating some forms of hereditary ataxia. This will be the first clinical trial testing varenicline in patients with Parkinson Disease. The specific nicotinic cholinergic receptors varenicline targets are located in the human striatum with afferent cholinergic input arising from the brainstem where the locomotor center of the brain is thought to originate. The direct and indirect effects on these receptors may provide a mechanism to improve postural instability and imbalance in this patient population.

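### The primary test is a before/after paired t-test, which does not compare varenicline with placebo and so cannot test the trial's stated null hypothesis

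*Combined protocol and SAP*

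**What the plan says.** The Primary Objective section sets a comparative hypothesis, that "varenicline will result in improvement of balance and postural instability after eight weeks of treatment compared to placebo". Its null is that "there will be no difference in tests of balance between subjects on placebo compared to those on varenicline", with the Berg Balance Scale (BBS) as the measure. The Study Design section describes a parallel-group, placebo-controlled trial.

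The Aim 1 bullet of the Outcomes and Data Analysis section names the test: "The primary hypothesis will be tested using a paired *t*-test using means of the total Berg Balance Scale score before and after treatment". The next sentence adds a regression: "Linear regression will be used to determine if there is an association among outcome, gender, age, race, or ethnicity". Aim 2 follows the same pattern: "Secondary hypotheses will be tested using paired *t*-tests on the full MDS-UPDRS, the TUG, and the ABC scale".

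Under Sample Size and Accrual the trial is sized differently: "a sample size of 19 subjects for each group would be needed for a parallel design". The inputs are a difference of 8 points, SD 8.48, two-sided 0.05 and power 0.80.

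**The concern.** A paired t-test asks whether subjects' scores changed between two visits. The primary hypothesis asks whether scores changed more on varenicline than on placebo. The plan does not say whether the paired test is run in the varenicline arm, in each arm, or in all subjects together, but in none of these forms does treatment arm enter the test.

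Anything that moves both arms alike is then open to being read as efficacy. That includes placebo response, familiarity with the BBS tasks at a second testing, and possibly regression to the mean, since entry requires a recent fall or near fall. Randomisation and the placebo group exist to remove these influences, and the stated efficacy test makes no use of that comparison. Type I error for the stated null is not controlled, and the 0.80 power belongs to a test the plan does not name.

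**Working it through.** **1. Reproduce the sample size.** Inputs from Sample Size and Accrual: difference 8, SD 8.48, two-sided 0.05, power 0.80.

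- Standardised difference: 8 / 8.48 = 0.943.
- Two-sample, normal approximation: 2 × [8.48 × (1.960 + 0.842) / 8]² = 17.6 per arm.
- Two-sample, t distribution: 18.65, rounded up to 19 per arm. Power at 19 is 0.808.
- Paired t-test with SD of change 8.48: 10.9, so 11 pairs.

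The plan's 19 per group is thus a two-sample figure and does not come from the paired test.

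**2. Look for a between-arm BBS test elsewhere.**

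- The Aim 1 regression lists gender, age, race and ethnicity. It includes neither arm nor baseline BBS.
- The Aim 2 logistic regression names treatment arm, but as the outcome, in a side-effect analysis without the BBS.
- Aim 3 compares treated with untreated subjects, for adverse events only.
- The intent-to-treat statement says who is analysed, not which contrast is tested.

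No such test is stated.

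**3. How often the paired test favours the drug when there is no drug effect.** Assumptions, none given in the documents: normal scores, SD 8.48 at both visits, correlation r between visits, and an equal mean gain g in both arms.

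- SD of change = 8.48 × √[2(1 − r)], which is 8.48, 6.57 and 5.36 for r = 0.5, 0.7 and 0.8.
- The t statistic is noncentral with parameter g√n / SD of change. For g = 3, r = 0.7, n = 19: 3 × 4.359 / 6.57 = 1.99, against a critical value of 2.10 on 18 df. The probability of exceeding it is 0.47.

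Percentage of trials significant in the drug's favour at two-sided 0.05:

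| Shared gain (points) | n = 19, r = 0.5 / 0.7 / 0.8 | Pooled n = 38, r = 0.5 / 0.7 / 0.8 |
|---|---|---|
| 0 | 2.5 / 2.5 / 2.5 | 2.5 / 2.5 / 2.5 |
| 1 | 7.0 / 9.2 / 11.7 | 10.5 / 14.8 / 20.0 |
| 2 | 16.2 / 24.1 / 33.7 | 29.3 / 44.8 / 61.0 |
| 3 | 30.9 / 47.0 / 63.6 | 56.5 / 78.3 / 91.9 |
| 4 | 49.4 / 70.9 / 86.7 | 80.8 / 95.5 / 99.4 |

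**4. The informal rule: significant on drug, not significant on placebo.** With independent arms and equal gains the probability is p(1 − p). At r = 0.7 and 3 points: 0.470 × 0.530 = 0.25. Simulation (100,000 trials per setting) gives 18%, 25% and 21% at 2, 3 and 4 points for r = 0.7, and 12% to 25% over r = 0.5 to 0.8. Running the paired test separately in each arm therefore does not repair the problem.

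**5. A between-arm test.** In the same simulations a two-sample t-test on change rejects in about 5% of trials (4.9% to 5.1%) whatever the shared gain.

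- With 19 per arm and SD 8.48, the difference detectable at 80% power is 7.92 points.
- Adjusting for baseline multiplies the SD by √(1 − r²). This gives 7.92 × 0.866 = 6.9 (r = 0.5), 7.92 × 0.714 = 5.7 (r = 0.7) and 7.92 × 0.600 = 4.8 (r = 0.8). The one degree of freedom spent on the covariate is ignored.
- Power for 8 points with ANCOVA is 0.90 at r = 0.5 and 0.98 at r = 0.7.

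**The case against.** The strongest reply is that the intent is plain. Objectives, design and sample size all point to a between-arm comparison, so the paired test may simply be misnamed. That may be so, but the sentence specifies scores before and after treatment, and Aim 2 repeats the paired test. As written, the analyst must choose the test and the arm or arms after unblinding.

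Several narrower points stand in part:

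- **Small gains.** A shared gain need not reach significance. At 1 point the n = 19 test favours the drug in 7% to 12% of trials over r = 0.5 to 0.8. The defect is that the test cannot separate shared gain from drug effect, not that every gain produces a false claim.
- **Assumptions.** The percentages rest wholly on assumed gains and correlations. They illustrate the risk and do not predict it.
- **Regression to the mean.** Entry is by fall history, not by a low BBS score, so some regression is plausible but its size cannot be judged.
- **Use of placebo data.** Adverse events are compared between arms, and two readings of the paired test would include placebo BBS scores. What is missing is the efficacy contrast.
- **The 8-point definition of improvement** in the Berg Balance Scale section. If applied to the arm mean, a 3-point shared gain would seldom reach it: at r = 0.5 the standard error is 8.48 / √19 = 1.95, and (8 − 3) / 1.95 = 2.57, about 0.5%. The analysis section does not tie this threshold to the test, and it would still compare nothing with placebo.
- **Choice of remedy.** A two-sample t-test on change would also be valid and matches the stated outcome. ANCOVA is preferred for precision and is not the only repair.

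**Conclusion.** The concern holds and must be fixed. The stated primary analysis does not test the stated null, and the document contains no between-arm test of the BBS. This conclusion follows from the text and needs no numerical assumption.

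The size does rest on assumptions: no drug effect, SD 8.48 at both visits, r between 0.5 and 0.8, and equal gains in both arms. A 3-point shared gain would then give a significant result in the drug's favour in 31% to 64% of trials with the test in 19 varenicline subjects, and in 57% to 92% if both arms are pooled. A between-arm test holds about 5%. The same fault affects MDS-UPDRS, TUG and ABC.

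**What to change.** Replace the Aim 1 test with ANCOVA: week 9 BBS as outcome, treatment arm as factor, baseline BBS as covariate, two-sided 0.05. Report the adjusted mean difference between arms with its 95% confidence interval. If the sponsor prefers to keep change as the analysed variable, a two-sample t-test on change is an acceptable but usually less precise alternative. Name one of the two in advance.

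In addition:

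- Use the same model for MDS-UPDRS, TUG and ABC, each with its own baseline.
- Add arm and baseline BBS to the exploratory regression on age, gender, race and ethnicity.
- Keep any paired before/after results as description within arm, with no inference about the drug.
- State that the 0.80 power (19 per arm, 8 points, SD 8.48) refers to the between-arm comparison. It is conservative under ANCOVA if the correlation with baseline is material. At r = 0.3 the gain is slight: 7.92 × √(1 − 0.09) = 7.6 points.

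The cost is rewording the analysis section. Rating scales are already collected at entry and week 9, and the planned 42 subjects suffice.

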### Sample Size and Population

Sample size is estimated to be 38 patients; however 42 will be recruited to allow for attrition. All patients will have been diagnosed with PD using the UK Brain Bank Criteria. There will be no stratification of randomization.

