### Secondary Objectives

There are two secondary hypotheses. First, we hypothesize that subjects with the postural-instability-gait disturbance (PIGD) subtype of PD will be more responsive to treatment compared to the tremor-predominant subtype. Patients will be categorized with tremor-predominant PD if the ratio of the mean tremor score to the mean PIGD score is 1.5 or higher and as PIGD predominant if the ratio is 1 or lower. The mean PIGD score

will be defined as the sum of an individual's baseline falling, freezing, walking, gait and postural stability UPDRS scores divided by five.

The second hypothesis is that varenicline will improve cognitive functioning in PD subjects. This hypothesis will be tested by comparing the results from the MMSE and the FAB at the beginning of the study, at four weeks, and at eight weeks.

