### SELECTION AND ENROLLMENT OF SUBJECTS

Inclusion criteria:

- Subjects will be diagnosed with Parkinson Disease (PD) by the UK Brain Bank criteria.
- Subjects will have to be at least stage 2 on the Hoehn and Yahr staging system of PD and have a history of at least 1 fall or near fall in the last 6 months.
- Subjects must have a stable medication regimen.
- All subjects will be over the age of 40 in an attempt to exclude inherited forms of parkinsonism.
- Serum creatine kinase, complete metabolic panel, complete blood count, liver function tests, renal function tests, platelets and EKG are within normal limits (results obtained from primary care physician and dated within the past 6 months or obtained at screening visit).

Exclusion criteria:

- Hoehn and Yahr stage 5 subjects.
- Subjects with a history of major psychiatric disorder, deep brain stimulation surgery, recent cerebral trauma, cardiac arrhythmia, or renal insufficiency.
- a cardiovascular procedure in the last 5 years (eg, percutaneous transluminal coronary angioplasty) or have cardiovascular instability (including myocardial infarction or unstable angina). Other cardiovascular exclusions include uncontrolled hypertension, significant neurological sequelae of cerebrovascular disease, peripheral vascular disease with prior amputation, or severe congestive heart failure (New York Heart Association class III or IV). Concurrent treatment with any MAOIs, bupropion (Wellbutrin), or nicotine patches.
- Dementia or other psychiatric illness that prevents the patient from giving informed consent (MMSE score less than 25).
- Concurrent treatment with trihexyphenidyl (Artane) or benzotropine mesylate (Cogentin).
- Significant degree of dysphagia, by history.

- Legal incapacity or limited legal capacity.
- Presence of severe renal disease (BUN 50% greater than normal or creatinine clearance <60 mL/min) or hepatic disease.
- Abnormal creatine kinase and/or platelet count in the past 6 months (as determined by lab reports obtained from primary care physicians or conducted at baseline).
- Use of varenicline within the previous 30 days.
- Women of childbearing potential who are pregnant at the time of screening or who will not use adequate contraception during participation in the study.
- Allergy/sensitivity to the drug or its formulations.
- Concurrent participation in another clinical study.
- Active substance or tobacco use or dependence.
- moderate or severe chronic obstructive pulmonary disease

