### CLINICAL AND LABORATORY EVALUATIONS

#### Timing of Evaluations

Subjects will be consented and have initial laboratory studies and rating scales at the entry visit. Once on the study medication, they will be contacted by phone at three weeks for questions regarding side effects, clinical issues, and to answer any questions. The subject will be reassessed after five weeks for depression or suicidal ideation, and they will continue with the intervention or placebo. Again, they will be contacted by phone at week seven to assess for safety and tolerability. They will be seen at nine weeks and outcome measures will be performed.

Table 1. Timing of Evaluations

Evaluation	Screening	Entry	Week 3	Week 5	Week 7	Week 9
Informed Consent		X				
Documentation of PD	X					
Medical/Treatment Hx	X					
Inclusion/Exclusion	X					
Clinical Assessment		X				
Neurological Exam		X				
Adherence Assessments			X	X	X	X
Questionnaires						
MDS-UPDRS and other rating scales		X				X
Beck Depression/suicide scales		X		X		X
Mental Status exam		X				X
FAB		X				X
EKG		X				

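### The tests named for the secondary hypotheses do not compare drug with placebo and address neither the subtype nor the cognition hypothesis

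*Combined protocol and SAP*

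**What the plan says.** Under Secondary Objectives the protocol states two hypotheses. The first is that "subjects with the postural-instability-gait disturbance (PIGD) subtype of PD will be more responsive to treatment compared to the tremor-predominant subtype". Subtype is defined by the ratio of mean tremor score to mean PIGD score: 1.5 or higher is tremor-predominant, 1 or lower is PIGD. The second is that varenicline improves cognition, to be examined by "comparing the results from the MMSE and the FAB at the beginning of the study, at four weeks, and at eight weeks". No test and no comparison of arms is named there.

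Under Outcomes and Data Analysis, the Aim 2 bullet says the secondary hypotheses will be tested by paired t-tests "on the full MDS-UPDRS, the TUG, and the ABC scale". MMSE and FAB appear in that bullet only in a side-effect analysis: "logistic regression will be performed with the treatment arm as the dichotomous outcome and the MMSE and FAB as covariates", with gender and age added. The only explicit treated-versus-untreated comparison in the section is for adverse events (Aim 3).

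The Study Design section states: "This is a randomized, double blind, placebo controlled parallel-designed study". On allocation, Sample Size and Population says: "There will be no stratification of randomization". In Table 1 (Timing of Evaluations), the "Mental Status exam" and FAB rows are marked at Entry and Week 9 only.

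**The concern.** The hypotheses and the tests do not match. One hypothesis asks whether the treatment effect differs between subtypes, which needs an arm-by-subtype contrast. The other asks whether drug improves cognition, which needs a drug-placebo difference on MMSE and FAB. The named tests are on three other scales and make neither comparison.

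The test itself is also wrong for the design. A paired test on before and after scores attributes all change to treatment. Placebo response, practice and regression to the mean can move both arms. Regression to the mean is plausible here because subjects must "have a history of at least 1 fall or near fall in the last 6 months", which selects people at a bad time.

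Followed as written, the plan could report change shared with placebo as a drug effect on MDS-UPDRS, TUG or ABC. It would produce no result for either stated secondary hypothesis. Any analysis that filled the gap would be chosen later, possibly after unblinding.

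**Working it through.** **The plan's own figure.** Inputs from Sample Size and Accrual: difference 8 BBS points, SD 8.48, two-sided 0.05, power 0.80. The standardised difference is 8/8.48 = 0.943. A two-sample t-test then needs 18.65 per arm, rounded up to 19; power is 0.785 at 18 and 0.808 at 19. The stated 19 per group reproduces. The trial was therefore sized for a between-arm comparison, which the paired tests do not make.

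**Paired tests when the drug does nothing.** Assumption: both arms change equally by d = mean change / SD of change. The documents give no value for d, so a range is shown. Rejection rates come from the noncentral t with n − 1 df and noncentrality d√n. The two arms are independent, so the chance of a significant result on drug but not on placebo is p(1 − p), where p is the drug-arm rate; a simulation of 40,000 trials agreed (0.147, 0.251, 0.111).

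| d | Drug arm only, n = 19 | Both arms pooled, n = 38 | Significant on drug, not on placebo | Between-arm t-test |
|---|---|---|---|---|
| 0.25 | 0.178 | 0.324 | 0.147 | 0.05 |
| 0.50 | 0.541 | 0.851 | 0.251 | 0.05 |
| 0.75 | 0.871 | 0.995 | 0.111 | 0.05 |

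The plan does not say whether the paired test is run in the drug arm, in each arm or on everyone, so all three readings are shown. All three exceed 5% at every d.

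**Subtype hypothesis, once an interaction is fitted.** Assumptions: outcome BBS with SD 8.48, N = 38, everyone classifiable, arms balanced within subtype. With n_P PIGD and n_T tremor-predominant subjects,

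SE = 2 × SD × √(1/n_P + 1/n_T), half-width = t(34) × SE, t(34) = 2.032.

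| Split | SE | 95% half-width | Power for an 8-point interaction |
|---|---|---|---|
| 50/50 | 16.96 × √(2/19) = 5.50 | 11.2 | 0.293 |
| 80/20 | 16.96 × √(1/30.4 + 1/7.6) = 6.88 | 14.0 | 0.204 |
| 90/10 | 16.96 × √(1/34.2 + 1/3.8) = 9.17 | 18.6 | 0.136 |

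The SE of the overall arm difference is 8.48 × √(2/19) = 2.75, so these are 2.0, 2.5 and 3.3 times as large. Baseline adjustment multiplies the SD by √(1 − r²), with 33 df. For assumed r from 0.5 to 0.8, the half-width runs from 6.7 (r = 0.8, 50/50) to 16.2 (r = 0.5, 90/10), and power from 0.653 down to 0.165.

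Balance within subtype is not guaranteed, since randomisation is unstratified. Assume 19/19 allocation:
- Split 30/8: the eight divide 6/2 or worse with probability 2 × (0.0949 + 0.0196 + 0.0015) = 0.232. At 4/4 the half-width is 13.7; at 6/2 it is 8.48 × √(1/13 + 1/17 + 1/6 + 1/2) × 2.032 = 15.4.
- Split 34/4: all four fall in one arm with probability 2 × 3876/73815 = 0.105, and the interaction cannot then be estimated.

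Subjects with a ratio between 1 and 1.5 belong to neither subtype, so the usable N may be below 38 and precision worse.

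**Cognition.** No figure can be given. The documents state no SD or effect size for MMSE or FAB, and an MMSE below 25 is an exclusion.

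**Schedule, side by side.** Secondary Objectives uses MMSE and FAB at baseline, four and eight weeks. Table 1 has both at Entry and Week 9 only. On-Study Evaluations has the movement and cognitive scales done twice. Interventions, Administration, and Duration puts the outcome measures, without naming scales, at the end of week 5 and at study end.

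**The case against.** The strongest reply is that the wording is loose and an arm comparison was intended. The phrase about before and after treatment belongs to the primary-outcome bullet, the primary null hypothesis is stated as placebo against varenicline, and the sample size is for a parallel design. It is true that before/after is inferred for the secondary tests. But drug and placebo subjects are not pairs, so no other reading of a paired test fits the design. If a between-arm test was intended, the plan should say so.

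Second, the logistic regression does relate arm to MMSE and FAB and could show an association if Week 9 or change scores were entered. The plan does not say which scores enter. The model has arm as the dependent variable, is labelled a side-effect analysis, and gives no treatment difference on either scale.

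Third, the plan concedes power below 0.8 for secondary outcomes. That deserves credit, but it concerns precision and does not supply a missing contrast.

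Fourth, four and eight weeks may be counted from the end of the escalation week, making them Weeks 5 and 9. That would remove the conflict with the week 5 assessment, but Table 1 would still have no mid-study MMSE or FAB.

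What stands: the changes of 0.25 to 0.75 SD, the subtype splits and the correlations are assumptions; nothing in the plan says the arms are pooled; and 8.48 is the SD of a score, not of a change. Any between-arm test would cure the main defect, so ANCOVA is a choice of the better one.

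**Conclusion.** The concern holds. The named tests give no drug-placebo contrast, no subtype term and no cognitive outcome, so neither secondary hypothesis has a test that addresses it. This is an analysis that is wrong as written, not merely a missing detail.

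Without pooling, and with no drug effect, the chance of a significant drug-arm change is 18% to 87% over the assumed range, against 5% for a between-arm test. That rests on equal change in both arms. The absence of a subtype or cognition analysis rests on the text alone and needs no assumption.

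The subtype hypothesis can be estimated but hardly tested at this size, which is why the interaction should be labelled exploratory. The point should be corrected. It concerns secondary outcomes here, though the primary-outcome bullet also specifies a paired t-test and should be read with the same question in mind.

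**What to change.** 1. Replace the paired t-tests on MDS-UPDRS, TUG and ABC with a between-arm ANCOVA of the Week 9 score, adjusted for that scale's baseline.
2. Add the same ANCOVA for Week 9 MMSE and Week 9 FAB as the test of the cognition hypothesis, and say how the two scales together decide it. The logistic regression may stay as a side-effect analysis but should not serve this purpose.
3. For the subtype hypothesis, estimate the arm-by-subtype interaction adjusted for baseline, report it with a 95% confidence interval and call it exploratory. The protocol names no outcome for it; BBS, as the primary, is the natural one. State in advance how ratios between 1 and 1.5 are handled.
4. Reconcile the MMSE and FAB time points in Secondary Objectives with Table 1, and bring On-Study Evaluations and the week 5 sentence into line. If a mid-study assessment is kept, say how it is analysed.

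Cost: analysis wording only, since the Entry and Week 9 scores are already planned, plus a little more analysis work and an interaction interval that will be wide. Keeping mid-study MMSE and FAB would lengthen the Week 5 visit slightly.

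### The planned side-effect regression has treatment arm as its outcome and contains no adverse event, and it is the only model in the statistical section that uses MMSE and FAB

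*Combined protocol and SAP*

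**What the plan says.** The secondary-outcome paragraph (Outcomes and Data Analysis, Aim 2) specifies: "For side effect analysis, logistic regression will be performed with the treatment arm as the dichotomous outcome and the MMSE and FAB as covariates". It continues: "In addition, gender and age will also be included as covariates". It does not say whether the MMSE and FAB scores are from entry, from the final visit, or changes between the two.

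The same paragraph names paired t-tests for the secondary hypotheses, carried out "on the full MDS-UPDRS, the TUG, and the ABC scale". MMSE and FAB are not in that list.

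Secondary Objectives sets the cognitive aim: "The second hypothesis is that varenicline will improve cognitive functioning in PD subjects". It is to be tested by "comparing the results from the MMSE and the FAB at the beginning of the study, at four weeks, and at eight weeks". No placebo comparison and no statistical test is named there.

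Adverse events have their own paragraph (Aim 3). They are to be "classified as to seriousness of the side effect and likelihood that the side effect is related to the drug", and then compared between the treated and untreated groups, with no test named. General Design Issues adds: "The independent medical monitor will review adverse event data and the final analysis".

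**The concern.** In a randomized trial the arm is set by design and the events follow it. A side-effect analysis therefore needs the event as outcome and the arm as predictor. The planned model makes the arm the outcome and leaves the events out.

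Two things are at stake. First, an analyst who follows the sentence produces a result labelled as side-effect analysis that holds no information on side effects. Second, MMSE and FAB appear in no other analysis in the statistical section, so one of only two secondary hypotheses rests on a model that was not written to test it. The sentence may be a transposition of outcome and predictor, or a cognition test under the wrong label. Nothing elsewhere in the document settles which, and the two readings lead to different analyses.

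**Working it through.** **Reproducible design figure.** The plan gives no figure for this analysis; the only one to check is the primary sample size. With a difference of 8, SD 8.48, two-sided 0.05 and power 0.80, the normal formula gives 2 × (1.960 + 0.842)² × (8.48/8)² = 17.6, so 18 per arm. The t-based calculation gives 18.65, so 19 per arm as stated (power 0.808). The point below does not depend on it.

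**The model as written.** logit P(varenicline) = b0 + b1·MMSE + b2·FAB + b3·gender + b4·age. Adverse events in the model: 0 of 4 covariates. No coefficient can respond to an event rate.

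**Illustration for side effects** (1,500 runs, 21 per arm, assumed MMSE–FAB correlation 0.5, assumed placebo event rate 10%, no effect on cognition):

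| Event rate on varenicline | MMSE term significant | Joint MMSE + FAB test | Fisher's test on events |
|---|---|---|---|
| 10% | 0.045 | 0.063 | 0.016 |
| 30% | 0.050 | 0.067 | 0.25 |
| 50% | 0.053 | 0.078 | 0.75 |

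The planned model stays near its null rate throughout.

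**Read as a cognition test.** Take normal scores with unit SD, correlation r, equal covariance in both arms, and covariates unrelated to arm. The MMSE coefficient is then (dM − r·dF)/(1 − r²), where dM and dF are the true shifts on MMSE and FAB. With shifts of 0.8 SD:

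- Both improve: r = 0.3 gives (0.8 − 0.24)/0.91 = 0.62; r = 0.6 gives (0.8 − 0.48)/0.64 = 0.50.
- MMSE only: 0.8/0.91 = 0.88; 0.8/0.64 = 1.25.
- FAB only: −0.24/0.91 = −0.26; −0.48/0.64 = −0.75.

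The coefficient shrinks when both scales improve, and it turns negative when FAB alone improves although MMSE has not changed.

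**Simulation** (3,000 runs per setting; 42 subjects, 1:1; two-sided 0.05; final-visit scores unless noted; assumed MMSE–FAB correlation 0.3 or 0.6 and baseline–final correlation 0.5 or 0.7). Proportion significant, range over the four correlation settings:

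| True effect | MMSE term, planned model | Joint test (2 df), planned model | MMSE by arm, baseline-adjusted | MMSE by arm, unadjusted t |
|---|---|---|---|---|
| None | 0.04–0.06 | 0.07–0.08 | 0.05–0.06 | not tabulated |
| 0.8 SD on both | 0.19–0.37 | 0.73–0.83 | 0.83–0.94 | 0.71–0.73 |
| 0.8 SD on MMSE only | 0.70–0.85 | 0.67–0.83 | 0.82–0.94 | 0.71–0.72 |
| 0.8 SD on FAB only | 0.10–0.39 | not tabulated | 0.05–0.06 | not tabulated |
| 0.8 SD on both, entry scores in the model | 0.05 | not tabulated | not tabulated | not tabulated |

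In the FAB-only row, 0.10 to 0.39 of all trials show a significant apparent worsening of MMSE; almost none of the significant results point the other way. With entry scores the model can detect only chance imbalance.

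**Sensitivity.**

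- With 19 per arm and both scales improving, the figures are 0.16–0.33 against 0.78–0.91 baseline-adjusted.
- With integer scores capped at the scale maximum and entry MMSE of at least 25, they are 0.20–0.37 against 0.76–0.89.
- With FAB alone improving by less, the MMSE term is significant in 9–18% of trials at 0.5 SD and 6–9% at 0.3 SD (correlation pairs 0.3/0.5 and 0.6/0.7).
- With change scores in the planned model and 0.8 SD on both, the MMSE term reaches 0.37 and 0.27 at those two pairs. The joint test reaches 0.82 and 0.92, against 0.82 and 0.93 for baseline-adjusted MMSE.

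**The case against.** The strongest reply is that little depends on this sentence. Aim 3 already compares adverse events between groups, the medical monitor sees the event data, and neither uses the regression. This stands, and it limits the side-effect half to a wrong and redundant analysis. Aim 3 names no test, however, so it does not repair the sentence, and it does nothing for cognition.

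A second reply is that the sentence sits among the secondary outcomes and is naturally read as a cognition test. On final or change scores, a joint test of MMSE and FAB does compare the arms and keeps fair power; the large losses come from reading one conditional coefficient as if it were marginal. This is correct as far as it goes. But the plan names neither the joint test nor the time point. A joint test also does not say which scale changed, in which direction or by how much, and its null rejection rate here is 0.07 to 0.08.

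Third, the size of the loss depends on an assumed 0.8 SD effect, and the wrong-direction result fades at smaller effects. Part of the advantage of the direct comparison comes from baseline adjustment and not from reversing the model, as the unadjusted t-test column shows. Both points stand.

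Fourth, the listed t-tests are before–after tests, so adding MMSE and FAB to that list would not give a between-arm test either. That is true, and it is why the fix does not take that route.

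Finally, the plan already concedes: "Power for calculating secondary outcomes is lower than 0.8". Low power as such is not the complaint.

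**Conclusion.** The concern holds. As written, the side-effect regression cannot estimate an effect of varenicline on side effects. This follows from the specification alone and needs no assumption. It also leaves the second secondary hypothesis without a clear between-arm analysis. There is some between-arm information in the model if final or change scores are entered, so it would be too strong to say that no test exists.

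The cost under the cognition reading can only be illustrated, because the documents give no MMSE or FAB effect, SD or correlation. In the simulated settings it runs from little or no loss (MMSE alone improves, correlations 0.6/0.5: 0.85 against 0.82) to a fall from 0.83–0.94 to 0.19–0.37 (both improve). When only FAB improves there is also a risk of reporting a false cognitive decline.

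This should be corrected, but it is confined to secondary and safety analyses. The primary outcome and the Aim 3 comparison are unaffected.

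**What to change.** Delete the regression with arm as outcome and replace it with two statements.

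1. Side effects, under Aim 3: each type of adverse event (present or absent) is the outcome and arm is the predictor. Report counts by arm and a risk difference with 95% confidence interval for every event type, whatever its p-value. With 42 subjects, simple two-group comparisons will suit sparse events better than covariate-adjusted models. The exact layout of the table is a matter of preference.
2. Cognition, under Aim 2: MMSE and FAB at the final visit are each compared between arms, adjusted for the same scale's entry score, and this is named as the test of the second secondary hypothesis. Other between-arm models would also be valid, provided that the outcome is named and arm is the predictor.

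At the same time, reconcile the assessment times. Secondary Objectives uses MMSE and FAB at four weeks, Interventions, Administration, and Duration places outcome measures at the end of week 5, and Table 1 schedules the mental status exam and FAB only at entry and week 9.

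The cost is a few sentences and a longer safety table. Both scales are already scheduled at entry and the final visit, and adverse events are already recorded. The change should be made before the randomization is disclosed to the investigators.
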